At follow-up appointment these routine tests per standard of care before IVC filter removal will be performed:

- A physical exam
- · The study doctor will ask about medical history, how well patient is able to do daily activities, and if they are experiencing any possible symptoms related to the IVC filter placement such as abdominal or back pain.
- A rotation CT focused to the site of the filter will be performed as part of routine practice of filter removal. This is done to ensure the filter has not migrated or that the filter has not penetrated through the walls of the IVC such that filter retrieval would be unsafe.
- · IR physician will determine if patient status is stable and safe for IVC filter removal. If not, physician will discuss with primary care doctor if filter needs to remain permanently in patient or if later retrieval should be considered at subsequent follow up visits.
- · IVC filter retrieval will be performed under moderate sedation. This procedure is very similar in nature to the filter placement procedure. The IVC filter is removed via a similar process to the way in which it was placed. X-ray dye (contrast) will be injected around the filter to assure that the filter and the area beneath the filter are free of blood clots and that it is safe to proceed with removal. A catheter-based snare will be used to engage the hook at the end of the filter and the filter will then be enveloped by a removal sheath and removed from the body.

Imaging Analysis:

Single blind CT and x-ray imaging analysis will be conducted by a trained radiologist doctor using standard imaging tools and workstations (Agfa PACS V.6). The radiologist will be unaware which patient received which filter type to minimize any potential bias in searching for IVC filter complications.

The radiologist will be instructed to look for the following complications of the IVC filter per Society of Interventional Radiation (SIR) guidelines:

- Filter penetration as defined by more then 3mm penetration of IVC wall by one or more components of the IVC filter
 - o Also look for signs that other organs or spine were penetrated
- Filter tilt as defined by greater than 15 degrees tilt perpendicular to axis of IVC
- Filter migration as defined by more than 1 cm from initial filter location
- Filter thrombus as defined by clot formed in filter mesh
- Filter fracture as defined by breakage of one or more of filter components

0.1 Hunsthadia (Hala Tautumdatad 0./12).	

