8.0 Scientific Considerations	
☐ Phase I ☐ Phase II ☐ Phase III ☑ Phase IV	
7.2 If this is a clinical trial, check the applicable phase(s) (Help Text updated 9/13):	
would give two curves from time of insertion to time of CT scan showing penetration. The log rank statistic would look at comparisons over time. Finally, we will also do an analysis of struts counting penetration as one or more and use the total number of penetrating struts as a secondary analysis.	
A correlation test will be performed as well as a survival analysis where a failure is penetration. This	
For sample size, we determined that with \sim 75 patients per group and similar differences in incidence or penetration as our preliminary study (25) (22% & 10%) we will see a significant difference at the p = 0.05 level with power 80%. If the difference is a little wider (25% vs. 10%) we will see significance at 50 patients per group. This calculation is using a comparison of proportions test with a z-statistic.	
IVC filter penetration (defined as greater than 3mm) through the IVC wall be the primary complication we will be measuring.	
Statistical and Power Analysis	

|--|

This study has a hypothesis:

If yes, state the hypothesis or hypotheses:

We hypothesize that there is no significant difference in efficacy and complication rate between the Option and the Denali filter.

8.2 * List the specific aims:

- 1) Determine if there is any difference in filter tilt in the vena cava
- 2) Determine if there is any difference in caval penetration
- 3) Determine if there is any difference in physician satisfaction after filter deployment

8.3 Statistical analysis:

Statistical and Power Analysis

IVC filter penetration (defined as greater than 3mm) through the IVC wall be the primary complication we will be measuring.

For sample size, we determined that with \sim 75 patients per group and similar differences in incidence or penetration as our preliminary study (25) (22% & 10%) we will see a significant difference at the p = 0.05level with power 80%. If the difference is a little wider (25% vs. 10%) we will see significance at 50 patients per group. This calculation is using a comparison of proportions test with a z-statistic.

A correlation test will be performed as well as a survival analysis where a failure is penetration. This would give two curves from time of insertion to time of CT scan showing penetration. The log rank statistic would look at comparisons over time.	

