The purpose of the present study is to characterize the incidence, time-course, and magnitude of complications of two commonly used IVC filters. Patients who present to Interventional Radiology for IVC filter will be randomized to have either a Denali filter or an Option filter placed. Patients will then be contacted 30-days following filter placement to come for filter removal. If it is not clinically safe for a patient to have the filter removed after 30 days, other attempts will be made to schedule for filter removal at 30-day intervals until the filter is removed. The filter placement and filter removal will be performed in the usual fashion according to the standards of our current practice. Upon filter removal, note will be made to potential complications including: filter perforation, filter migration, filter fracture and thrombus within the filter. Another main purpose of the study is to try to increase the numbers of patients who return promptly for filter removal. Many patients continue to have IVC filters in place for far longer than is needed due to poor follow up procedures and lack of tracking due to many patients being referred in from other services.

Little is presently known regarding the complication tendency of the relatively new Denali conical retrievable IVC filter (Cook, Bloomington, Indiana). The Option has been researched more and has been found to have a slightly lower incidence of complications than other conical filters.

In a prospective multicenter study of 100 Option filters, investigators noted one case of penetration among 39 filters assessed during retrieval cavograms (12); however, penetration was not dealt with as a dedicated endpoint. The option studies also did not randomize what filter was used and the data was only examined retrospectively with varying timepoints. The Denali was approved under an FDA "similar device" exemption so has not been subject to systematic long term study. The present study aims to characterize the incidence and time course of penetration and other complications at regular intervals for the Option filter compared with the Denali.

9.2 Preliminary studies:

The department of interventional radiology at UCSF has recently conducted retrospective comparative studies of IVC filter complications, comparing two devices in two separate studies. This research has inspired us to propose a randomized prospective trial to more clearly evaluate the efficacy of two newer IVC filters.

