Single blind CT and x-ray imaging analysis will be conducted by a trained radiologist doctor using standard imaging tools and workstations (Agfa PACS V.6). The radiologist will be unaware which patient received which filter type to minimize any potential bias in searching for IVC filter complications. The radiologist will be instructed to look for the following complications of the IVC filter per Society of

Filter penetration as defined by more then 3mm penetration of IVC wall by one or more

- components of the IVC filter
 - o Also look for signs that other organs or spine were penetrated
- Filter tilt as defined by greater than 15 degrees tilt perpendicular to axis of IVC
- Filter migration as defined by more than 1 cm from initial filter location
- Filter thrombus as defined by clot formed in filter mesh
- Filter fracture as defined by breakage of one or more of filter components

Statistics will be compiled and analysis will be performed by statistician using SPSS software.

Statistical and Power Analysis

Interventional Radiation (SIR) guidelines:

IVC filter penetration (defined as greater than 3mm) through the IVC wall be the primary complication we will be measuring.

For sample size, we determined that with \sim 75 patients per group and similar differences in incidence or penetration as our preliminary study (25) (22% & 10%) we will see a significant difference at the p = 0.05 level with power 80%. If the difference is a little wider (25% vs. 10%) we will see significance at 50 patients per group. This calculation is using a comparison of proportions test with a z-statistic.

A correlation test will be performed as well as a survival analysis where a failure is penetration. This would give two curves from time of insertion to time of CT scan showing penetration. The log rank statistic would look at comparisons over time.

Finally, we will also do an analysis of struts counting penetration as one or more and use the total number of penetrating struts as a secondary analysis.	
If you have a procedure table, attach it to the submission with your other study documents.	
14.2 Interviews, questionnaires, and/or surveys will be administered or focus groups will be condu	ıcted:
⊙ Yes C No	
List any standard instruments used for this study:	
Questionnaire given to IR docs after filter placement	
Attach any non-standard instruments at the end of the application.	
14.3 Conduct of study procedures or tests off-site by non-UCSF personnel:	
C Yes O No	

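### The imaging reader is said to be unaware of filter type but must inspect the filter itself, and no masking step is described, so the blind on the primary outcome cannot be relied on

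*Combined protocol and SAP*

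**What the plan says.** Section 7.1 (Imaging Analysis), repeated in 14.1, states: "Single blind CT and x-ray imaging analysis will be conducted by a trained radiologist doctor using standard imaging tools and workstations". It then says: "The radiologist will be unaware which patient received which filter type to minimize any potential bias in searching for IVC filter complications".

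The same list sets the reader's tasks. Penetration is defined as "Filter penetration as defined by more then 3mm penetration of IVC wall by one or more components of the IVC filter", and section 8.3 makes it the main outcome: "IVC filter penetration (defined as greater than 3mm) through the IVC wall be the primary complication". The reader also judges tilt (over 15 degrees), migration (over 1 cm from the initial location), thrombus in the mesh, and "Filter fracture as defined by breakage of one or more of filter components". Section 14.1 adds a secondary strut count: "Finally, we will also do an analysis of struts counting penetration as one or more and use the total number" of struts that penetrate.

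The arms are two products from two manufacturers (7.1). The follow-up scan is a rotational CT aimed at the filter site. Section 14.8 places an independent radiologist on the study staff for the imaging analysis. Section 9.1 separately says: "Upon filter removal, note will be made to potential complications including: filter perforation, filter migration, filter fracture and thrombus within the filter".

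**The concern.** Not telling a reader the allocation protects an assessment when the treatment leaves no trace in the material being read. Here the material is an image of the treatment. The reader cannot score penetration, thrombus in the mesh, fracture or the strut count without looking closely at the device. If the two filters are recognisable, the reader knows the arm whatever the envelope procedure conceals.

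The plan states unawareness as a fact but describes nothing that would secure it: no de-identified export, no hiding of reports or placement images, no second reader or adjudication, no agreement measure, and no check on whether the blind held. Migration is judged against the initial location, so some placement information must also reach the reader, and no masking of that is described.

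Penetration is a yes/no call at 3 mm, with no plane or measurement method given. Borderline calls could move in one arm, creating a difference or hiding one. Once images have been read this way, with no measurements kept, blinded assessment cannot be claimed afterwards.

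**Working it through.** **Text.** The claim and the task can be set side by side.

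| Element | Where | Bearing on the blind |
|---|---|---|
| Reader unaware of filter type | 7.1, 14.1 | The claim |
| CT and x-ray on the standard PACS | 7.1, 14.1 | Device is in view; no masking step |
| Penetration over 3 mm by any component (primary) | 7.1, 8.3 | Components must be inspected |
| Fracture, thrombus in mesh, strut count | 7.1, 8.3, 14.1 | Components must be inspected |
| Two manufacturers' products | 7.1 | Recognition is plausible |
| Both filters grouped only as conical | 9.1 | Appearance on imaging not described |
| Independent radiologist | 14.8 | Partial protection |
| Limits of 3 mm, 15 degrees, 1 cm | 7.1, 14.1 | Partial protection |

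The plan gives no figure on this point to reproduce.

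**Illustration of what a failed blind could do.** Inputs from the plan: 75 per arm, two-proportion z-test, 5% level, and rates of 10% and 22% (8.3). A middle rate of 16% is (10 + 22)/2. Assumptions: a two-sided test, equal true rates *b* in both arms, all 75 per arm read, and recognition adding *s* points to the observed rate in one arm, so *a* = *b* + *s*.

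Approximate rejection probability:

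Φ[(s − 1.96·SE₀)/SE₁] + Φ[(−s − 1.96·SE₀)/SE₁]

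SE₀ = √(2p̄(1−p̄)/75), with p̄ = (a+b)/2

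SE₁ = √([a(1−a) + b(1−b)]/75)

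For *b* = 0.10 and *s* = 0.05: p̄ = 0.125; SE₀ = √(2 × 0.125 × 0.875/75) = 0.0540; SE₁ = √((0.1275 + 0.0900)/75) = 0.0539. The first term is Φ(−1.037) = 0.150 and the second is Φ(−2.894) = 0.002. The sum is 0.152.

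Exact binomial enumeration of the pooled two-sided test gives:

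| True rate, both arms | No shift | 5-point shift | 10-point shift |
|---|---|---|---|
| 10% | 5.1% | 15.2% | 41.0% |
| 16% | 5.1% | 12.5% | 32.5% |
| 22% | 5.0% | 10.8% | 27.9% |

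**A milder assumption.** Let the shift be extra false positives among non-penetrating filters only, so *a* = *b* + (1 − *b*)·*f*. The same approximation gives:

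| True rate | f = 2% | f = 5% | f = 10% |
|---|---|---|---|
| 10% | 6.4% | 13.3% | 34.6% |
| 16% | 5.9% | 10.2% | 24.8% |
| 22% | 5.6% | 8.6% | 19.2% |

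**The opposite direction.** With true rates of 22% and 10%, under-calling the higher arm by 5 points (to 17%) lowers the exact two-sided power at 75 per arm from about 53% to 24%. That the starting value is below the plan's stated 80% is a separate matter.

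**The case against.** **Recognition is not shown.** A reader might infer that the blind is impossible. That requires the two filters to look different on CT or x-ray. The documents name two manufacturers and call both filters conical; they do not describe how either appears on imaging. Counting penetrating struts does not require knowing the brand, and fracture is not the primary outcome. This stands: the supported claim is that the blind is not secured, not that it must fail.

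**Some protection exists.** A reader might also infer that nothing guards the primary outcome. That is too strong. Section 14.8 provides an independent radiologist, sections 7.1 and 14.1 intend that the reader not know the filter type, and the numeric limits narrow the room for judgement.

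**The endpoint source is largely settled.** The note made at removal (9.1) might be read as a rival, unmasked endpoint. However, sections 8.3 and 14.1 time the event to the CT scan that shows penetration, and 7.1 gives the definition to the imaging radiologist. The 9.1 sentence is background and does not say that the note enters any analysis. A line of confirmation is enough.

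**Direction and size are unknown.** Section 9.1 records slightly fewer complications for Option than for other conical filters, but it says little is known about Denali, and the stated hypothesis in section 8 is of no difference. No direction of bias is established. The shifts above are assumed, and at a 10% base a 10-point shift doubles the rate.

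None of this removes the core problem: the plan asserts unawareness while the task requires inspecting the randomised device, and no step makes the assertion achievable.

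**Conclusion.** The concern holds in limited form: the blind on the primary outcome cannot be relied on as described. The illustration (about 11% to 15% error for a 5-point shift and 28% to 41% for a 10-point shift, against a nominal 5%) shows that a modest reading shift would matter beside the planned 12-point difference (22% less 10%). It rests on equal true rates of 10% to 22%, 75 read per arm, a two-sided test and a shift confined to one arm. It does not estimate the bias in this trial. A 2% false-positive excess would leave the error near 6%. The documents support neither the conclusion that the filters are certainly distinguishable nor the conclusion that the read has no protection. The change is worth making before any image is read.

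**What to change.** In sections 7.1 and 14.1:

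1. Replace the assertion of unawareness. Describe an independent reader who is not told the assignment and takes no part in placement or retrieval, and state that device type may be recognisable on the images. Have the reader record a guess of filter type for each scan, so that the blind can be checked and reported.
2. Make the read a measurement. The reader records millimetres beyond the caval wall for each penetrating strut, the tilt angle and the displacement, by one fixed method for both devices. The statistician applies the 3 mm, 15 degree and 1 cm cut-offs afterwards.
3. Read de-identified images in shuffled order, with reports, placement notes and symptoms hidden. Supply only the placement image needed to judge migration.
4. Confirm that this CT read alone defines the penetration endpoint, and that notes made at removal are clinical data only.

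The cost is protocol wording, a reading form, some extra reading time, and a description of blinding that is less favourable but accurate. A measured value can still be biased near 3 mm if the device is recognised, so these steps reduce the bias and do not remove it.

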8.0 Scientific Considerations	
☐ Phase I ☐ Phase II ☐ Phase III ☑ Phase IV	
7.2 If this is a clinical trial, check the applicable phase(s) (Help Text updated 9/13):	
would give two curves from time of insertion to time of CT scan showing penetration. The log rank statistic would look at comparisons over time. Finally, we will also do an analysis of struts counting penetration as one or more and use the total number of penetrating struts as a secondary analysis.	
A correlation test will be performed as well as a survival analysis where a failure is penetration. This	
For sample size, we determined that with \sim 75 patients per group and similar differences in incidence or penetration as our preliminary study (25) (22% & 10%) we will see a significant difference at the p = 0.05 level with power 80%. If the difference is a little wider (25% vs. 10%) we will see significance at 50 patients per group. This calculation is using a comparison of proportions test with a z-statistic.	
IVC filter penetration (defined as greater than 3mm) through the IVC wall be the primary complication we will be measuring.	
Statistical and Power Analysis	

|--|

This study has a hypothesis:

If yes, state the hypothesis or hypotheses:

We hypothesize that there is no significant difference in efficacy and complication rate between the Option and the Denali filter.

8.2 * List the specific aims:

- 1) Determine if there is any difference in filter tilt in the vena cava
- 2) Determine if there is any difference in caval penetration
- 3) Determine if there is any difference in physician satisfaction after filter deployment

8.3 Statistical analysis:

Statistical and Power Analysis

IVC filter penetration (defined as greater than 3mm) through the IVC wall be the primary complication we will be measuring.

For sample size, we determined that with \sim 75 patients per group and similar differences in incidence or penetration as our preliminary study (25) (22% & 10%) we will see a significant difference at the p = 0.05level with power 80%. If the difference is a little wider (25% vs. 10%) we will see significance at 50 patients per group. This calculation is using a comparison of proportions test with a z-statistic.

A correlation test will be performed as well as a survival analysis where a failure is penetration. This would give two curves from time of insertion to time of CT scan showing penetration. The log rank statistic would look at comparisons over time.	
Finally, we will also do an analysis of struts counting penetration as one or more and use the total number of penetrating struts as a secondary analysis.	
8.4 If this study has undergone scientific or scholarly review, please indicate which entity perform review:	ed the
☐ Cancer Center Protocol Review Committee (PRC) (Full approval is required prior to final CHR approval for cancer-related protocols.)	
☐ CTSI Clinical Research Center (CRC) advisory committee	
▼ Departmental scientific review	
☐ Other:	
Specify Other:	

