top of the filter must sit below the renal veins so it doesn't cause obstruction of the renal veins. In addition, pictures of the IVC are taken to serve as another tool in measuring the diameter of the IVC to make sure the diameter of the IVC is less than 2.8cm. This is particularly important in situations when a CT or MRI of the abdomen and pelvis is not available to have reviewed prior to the procedure. Once pictures are obtained and it is made certain that the IVC diameter is less than 2.8cm, the filter will be inserted through the catheter, and placed below the renal veins. During the placement procedure, positioning of the filter will be monitored with x-ray pictures. At the completion of the procedure the catheter will be removed and pressure will be applied to the insertion site until the bleeding has stopped. All of this is part of routine standard of care for placement of the filter. The doctor performing the procedure will be asked to complete a short questionnaire after IVC filter placement which will be attached to "Study Documents".

Follow-Up:

After the IVC filter placement procedure patient status will be followed by the interventional radiology doctors.

Per standard of care after IVC filter placement, patient will be monitored in the hospital for up to 1 hour after the procedure. If patient is in stable condition and sedation has resolved, they will return home the same day or returned to their hospital rooms.

A tentative appointment for follow up and filter retrieval will be ordered by IR physician at time of filter placement in APEX. This will ensure that scheduling and study staff will be aware that further patient and primary care follow-up is required.

Patient primary care physician and/or relevant medical staff will be telephoned one month after IVC filter placement to determine if patient is medically stable and suitable for IVC filter removal.

If IR and other doctors agree that IVC filter removal is recommended, patient will be scheduled to return for follow-up imaging and filter retrieval. If patient is not medically stable or still at high risk for blood clots, we will attempt to schedule a follow up one month later. Close contact with primary physician and patient will be maintained to ensure that filter is removed as soon as possible. APEX scheduling will be used to make sure follow up is performed at regular intervals.

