Patient primary care physician and/or relevant medical staff will be telephoned one month after IVC filter placement to determine if patient is medically stable and suitable for IVC filter removal.

If IR and other doctors agree that IVC filter removal is recommended, patient will be scheduled to return for follow-up imaging and filter retrieval. If patient is not medically stable or still at high risk for blood clots, we will attempt to schedule a follow up one month later. Close contact with primary physician and patient will be maintained to ensure that filter is removed as soon as possible. APEX scheduling will be used to make sure follow up is performed at regular intervals.

At follow-up appointment these routine tests per standard of care before IVC filter removal will be performed:

- A physical exam
- · The study doctor will ask about medical history, how well patient is able to do daily activities, and if they are experiencing any possible symptoms related to the IVC filter placement such as abdominal or back pain.
- A rotation CT focused to the site of the filter will be performed as part of routine practice of filter removal. This is done to ensure the filter has not migrated or that the filter has not penetrated through the walls of the IVC such that filter retrieval would be unsafe.
- · IR physician will determine if patient status is stable and safe for IVC filter removal. If not, physician will discuss with primary care doctor if filter needs to remain permanently in patient or if later retrieval should be considered at subsequent follow up visits.
- · IVC filter retrieval will be performed under moderate sedation. This procedure is very similar in nature to the filter placement procedure. The IVC filter is removed via a similar process to the way in which it was placed. X-ray dye (contrast) will be injected around the filter to assure that the filter and the area beneath the filter are free of blood clots and that it is safe to proceed with removal. A catheter-based snare will be used to engage the hook at the end of the filter and the filter will then be enveloped by a removal sheath and removed from the body.

Imaging Analysis:

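### Failure is dated by the CT that shows penetration, but the CT schedule is contradictory; if most patients have one CT at retrieval, the planned Kaplan-Meier curves reflect scan timing, not the time course

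*Combined protocol and SAP*

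**What the plan says.** The time-to-event analysis is in section 8.3 and is repeated in 14.1: "A correlation test will be performed as well as a survival analysis where a failure is penetration". It gives "two curves from time of insertion to time of CT scan showing penetration. The log rank statistic would look at comparisons over time". No censoring rule and no interval-censored method is stated. The sample size rests on a different test: "This calculation is using a comparison of proportions test with a z-statistic".

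On CT timing, the sections point two ways.

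- **CT tied to retrieval.** Section 7.1, Follow-Up (repeated in 14.1): "A rotation CT focused to the site of the filter will be performed as part of routine practice of filter removal". The one-month contact is a call: "Patient primary care physician and/or relevant medical staff will be telephoned one month after IVC filter placement". Once removal is agreed, the "patient will be scheduled to return for follow-up imaging and filter retrieval". Section 9.1 adds "Upon filter removal, note will be made to potential complications", and what repeats monthly there is the scheduling attempt: "other attempts will be made to schedule for filter removal at 30-day intervals until the filter is removed". Section 10.4 treats loss to follow-up as missing both the imaging and the retrieval.
- **Serial CT.** Section 9.2 says the trial improves on the earlier retrospective study through regularly repeated imaging up to removal. Sections 7.1 and 14.1 list the CT among the tests at the follow-up appointment, before the decision to remove, and allow for later visits.

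Section 9.1 makes the time course of penetration part of the study's purpose.

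**The concern.** A CT shows whether a strut is through the wall on that day. It does not show when that happened. With one CT per patient, a positive patient is known only to have penetrated some time before the scan, and a negative patient only to be free up to it. These are current-status data. Entering the scan date as the failure date makes the Kaplan-Meier curve rise at the rate of scanning multiplied by the proportion already penetrated. Two identical penetration processes then give different curves when patients return at different times. The trial could publish a picture of retrieval scheduling as the time course of penetration.

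Serial CT removes most of this. Whether the planned analysis is sound therefore depends on a schedule that the plan does not settle.

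**Working it through.** **Inputs.** From the plan: failure time and log-rank test (8.3, 14.1); 22% and 10% penetration, about 75 per group, 5% level, 80% power (8.3, 10.4, 14.1). The plan gives no dwell times, so every schedule below is an assumption. Further assumptions: constant hazard with 22% penetrated at day 60, and scan timing unrelated to penetration.

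**1. The plan's own figure.** There is no event count, hazard ratio or power for the log-rank test. The only figure is about 75 per group for the z-test. By the usual pooled formula, 22% against 10% needs 146 per group two-sided (115 one-sided), and 75 per group gives 52% power (64% one-sided). That is a separate matter, and nothing below depends on it.

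**2. One CT per patient, continuous timing.** CT at 30 days plus an exponential delay, with median CT day m.

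- λ = −ln(0.78)/60 = 0.004141 and F(t) = 1 − exp(−λt), so F(30) = 11.7%, F(60) = 22.0%, F(90) = 31.1%.
- Scan rate μ = ln 2/(m − 30).
- Kaplan-Meier limit at day t = 1 − exp(−μ × ∫F from day 30 to t).
- To day 60: ∫F = 30 − (0.8832 − 0.7800)/0.004141 = 5.08.

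| Median CT day | μ | μ × 5.08 | Curve at day 60 (true 22.0%) |
|---|---|---|---|
| 45 | 0.0462 | 0.235 | 20.9% |
| 60 | 0.0231 | 0.117 | 11.1% |
| 75 | 0.0154 | 0.078 | 7.5% |
| 90 | 0.0116 | 0.059 | 5.7% |
| 120 | 0.0077 | 0.039 | 3.8% |

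The first row looks right only because the two curves happen to cross near day 60. To day 90, ∫F = 60 − (0.8832 − 0.6889)/0.004141 = 13.08, and 1 − exp(−0.0462 × 13.08) = 45% against a true 31%.

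**3. One CT per patient, 30-day visits, share p retrieved per visit.** The curve at day 60 is 1 − (1 − pF(30))(1 − pF(60)). For p = 0.3, 0.4 and 0.5 it reads 9.9%, 13.1% and 16.2%.

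**4. Partial serial CT.** Let a share q of the visits without retrieval also have a CT, and c = p + (1 − p)q. The curve at day 60 is
1 − (1 − cF(30)) × (1 − c[q(F(60) − F(30)) + (1 − q)F(60)]/[q(1 − F(30)) + 1 − q]).

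| q | p = 0.3 | p = 0.5 |
|---|---|---|
| 0 | 9.9% | 16.2% |
| 0.25 | 14.4% | 18.7% |
| 0.5 | 17.9% | 20.5% |
| 0.75 | 20.5% | 21.6% |
| 1 | 22.0% | 22.0% |

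**5. A different assumed setting.** 22% penetrated at month 6, and 30/20/15/15/10/10% of patients retrieved in months 1 to 6. By simulation the one-CT curve reads 1.2% at month 1 (true 4.1%) and 38.2% at month 6 (true 22.0%). If all penetration occurs in month 1, so that the true curve is flat at 22%, the one-CT curve still climbs from 6.6% to 48.6%. With monthly CT it reads 4.1% and 21.8% in the constant-hazard case.

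**6. Comparison of filters (simulation, 75 per arm).**

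- *Same timing in both arms, one CT each.* Log-rank type I error is about 5%. Power for 22% against 10% at day 60, log-rank against z-test: 45.6% against 56.2% (continuous schedule, median day 60), and 44–54% against 48–61% (30-day visits).
- *Scan rates differing by arm, ratio 1.5 or 2.* Log-rank type I error is 14–17% or 31–38%. The z-test stays near 5% if penetration is flat. If penetration rises with dwell time, it reaches 8% or 18% (continuous) and 12% or 32% (30-day visits).

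**7. Does an interval-censored estimate recover the curve?** Turnbull estimates at day 60 average 23.0, 21.4, 21.0, 20.3 and 19.0% for the five medians in step 2, and about 21% on 30-day visits. Their standard deviation is about 8 to 10 percentage points.

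**The case against.** The strongest reply is that section 9.2 is the only direct statement on how often imaging is done, and it promises repeated imaging expressly to improve on the earlier study. With a CT at every visit, the curves are right at visit days and the log-rank test is valid. Partial serial CT already helps: with a CT at three quarters of the non-retrieval visits, step 4 gives 20.5% to 21.6% against 22.0%. Time course appears in the background text and not among the three specific aims in 8.2, and the sample size uses the proportions test. Interval-censored curves are imprecise at this size.

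Much of this stands. The single-CT schedule is the more natural reading of the procedures, but it is not established. What remains is that no section says at which visits a CT is done, and the validity of the planned curves depends on the answer.

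A reader might also infer that the comparison of filters is biased. The documents do not support that. Both arms are randomised within one service under one follow-up procedure, and nothing shows that CT timing would differ by filter. If it did differ, the crude proportions test would share the problem whenever penetration rises with dwell time, as section 9.2 reports for an earlier filter.

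**Conclusion.** The concern holds in conditional form. Failure is dated by the CT, and the sections conflict on when that CT is done. If most patients have only one, the planned Kaplan-Meier curves cannot show the time course that section 9.1 sets as an aim. The size depends on dwell times that the plan does not give: 3.8% to 20.9% at day 60 against a true 22% over the continuous schedules tried, and 45% against 31% at day 90 in one of them. It would be wrong to infer that the curves always understate penetration, or that any visit without a CT ruins them. The error changes sign over time and shrinks steadily as more visits carry a CT.

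For the comparison of filters, the loss with equal timing is some power (4 to 11 points on the schedules tried), not validity. All figures assume that scan timing is unrelated to penetration. The point should be fixed. Confidence is medium, because it turns on which reading of the CT schedule is meant.

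**What to change.** 1. Reconcile sections 7.1, 9.1, 9.2, 10.4 and 14.1, and state at which visits a CT is done.
2. Unless a CT is done at essentially every visit, define penetration in 7.1, 8.3 and 14.1 as interval-censored, from the last negative CT (or insertion) to the first positive CT. Patients with no positive CT are censored at their last negative CT. Replace Kaplan-Meier and log-rank with an interval-censored method, for example Turnbull curves and an interval-censored regression on filter; no single model needs to be mandated. If CT at every visit is confirmed, Kaplan-Meier and log-rank can stay, with the censoring rule written down.
3. Report CT timing by arm, and the unadjusted proportions beside the model. State the assumption that scan timing is unrelated to penetration given filter. This includes the discontinuation, under section 17.1, of patients who are not retrieval candidates.

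**Cost.** Analysis wording and one statement of the CT schedule; the scan dates and results are already to be collected. The curves will be imprecise at 75 per arm. The method relies on scan timing being non-informative, so scans prompted by symptoms could bias it. Software beyond the SPSS named in 14.1 may be needed.
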